We have established the efficacy of this “hormone-challenge test for functional ER” in new mammary cancer models derived from STAT1^{-/-} mice (Fowler A. J Nucl Med. 2012; 53:1119-26). In ovary-intact mice, SSM2 tumors, which are ER⁺ but ET non-responsive, show no decrease in PgR (PgR-A and PgR-B) levels upon antiestrogen with Fulvestrant treatment, whereas SSM3 tumors, which are ER⁺ and ET responsive, show a great reduction in PgR levels. More notably, in the SSM3 ER⁺/ET-responsive tumors, both a large decrease in ¹⁸F-FFNP uptake after Fulvestrant treatment and a large increase in ¹⁸F-FFNP uptake are observed after estradiol. The average tumor-muscle (T/M) ratios increased from 3.6 for the untreated mice to 6.9 in SSM3 mice after 24 hours of estrogen stimulation. Therefore, an up or down change in ¹⁸F-FFNP T/M ratio in mammary tumors accurately predicted sensitivity to estrogen addition or deprivation therapy, respectively, and was able to distinguish between ER⁺/endocrine-responsive and ER⁺/endocrine non-responsive disease.

More recently, Chan et al. (manuscript in preparation) used the same model to follow the decrease in ¹⁸F-FFNP mammary tumor uptake in response to estrogen deprivation therapy by ovariectomy, which reduces tumor PgR levels. Notably, in this study, they compared PET imaging using ¹⁸F-FDG (to measure glucose uptake), ¹⁸F-FES (to measure ER levels), or ¹⁸F-FFNP (to measure PgR levels) to see which probe would best predict response to estrogen deprivation therapy. Uptake in endocrine-sensitive and -resistant mammary tumors (both of which were ER⁺) was measured by PET in mice before ovariectomy, and on days 3 and 4 after this form of estrogen deprivation therapy. Specificity of ¹⁸F-FFNP uptake in ER⁺ mammary tumors was determined by competition assays using unlabeled ligands for PgR and confirmed by IHC. The levels of ¹⁸F-FES and FDG tumor uptake remained unchanged in endocrine-sensitive or resistant tumors after estrogen deprivation therapy compared to those at pre-treatment. By contrast, estrogen deprivation therapy led to a reduction in PgR expression and ¹⁸F-FFNP uptake in endocrine-sensitive tumors, but not in endocrine-resistant tumors, as early as 3 days post-treatment, importantly demonstrating that *PgR-PET provides a more sensitive and robust measure of tumor response than ¹⁸F-FES- or ¹⁸F-FDG-PET.*

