2.0 OBJECTIVES

Our hypothesis is that change in ¹⁸F-FFNP uptake following 1-day of estradiol is a strong predictor of response to ET in patients with hormone-sensitive (ER⁺/± PgR⁺)/HER2- breast cancer. We believe the increase in tumor PgR after 1-day estradiol will be more reliable than a decrease after estrogen deprivation, particularly because most breast cancer patients are postmenopausal and basal PgR levels will be low due to the low endogenous, menopausal estrogen levels. Thus, we propose to use a hormone-challenge test for assessment of functional

ER based on the change in ^{18}F -FFNP uptake before and after a 1-day estradiol challenge in patients with ER+ metastatic breast cancer. We expect that the changes in ^{18}F -FFNP uptake to be a highly reliable means to predict a favorable response of ER+ breast cancer to ET. We propose to study patients with biopsy-proven new diagnosis of ER+ metastatic/recurrent breast cancer who are going to be treated with ET (tamoxifen, AI agents or faslodex) according to standard of care.

2.1. Evaluate whether the change in tumor uptake of ^{18}F -FFNP following a 1-day estradiol challenge differs among patients who respond to ET versus those who do not respond.

2.1.1 Determine the optimum cutoff value for change in tumor ^{18}F -FFNP uptake after estradiol to distinguish responders from nonresponders.

2.1.2 Evaluate whether the change in tumor uptake of FFNP can identify patients with hormone-sensitive disease who will respond to ET with greater sensitivity and selectivity than tumor PgR measured by IHC.

2.2 Evaluate the heterogeneity of tumor ^{18}F -FFNP uptake at baseline and after estradiol challenge in patients with multiple metastatic foci.

2.2.1. Explore whether response is related to ^{18}F -FFNP uptake heterogeneity. To assess the heterogeneity at the baseline, a comparison with FDG-PET/CT will be performed to map the metabolically active disease. Once the metabolically active disease is determined, FDG+/FFNP- will be considered as discordant lesions. At follow-up, the baseline FFNP-PET/CT will be correlated with follow-up FFNP-PET/CT to assess heterogeneity in response to estradiol.

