6.5 Image Analysis

The emission images will be corrected for measured attenuation using CT data according to the provide scanner manufacturer software package. FDG-PET/CT images will be evaluated and reported according to standard of care imaging procedures.

FFNP-PET/CT images will be evaluated by one observer qualitatively. PET images also will be evaluated semiquantitatively with the knowledge of the location of the lesion(s) by the use of the standardized uptake value (SUV) and tumor-to-normal tissue (T/N)

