ratio. The SUV is widely used for assessment of regional tracer accumulation in oncological studies, is technically simple to perform, and makes imaging easier for the patient because longer dynamic imaging is not required. SUV is a decay-corrected measurement of activity per volume of tissue (nCi/mL) divided by the average activity per unit mass in the entire body. The absolute change and the percent change in uptake of ^{18}F -FFNP will be assessed semiquantitatively and correlated with the clinical and radiologic results and subsequently with the results of the clinical follow-up evaluation. In patients with multiple lesions, the uptake up to 5 most intense lesions seen on PET images will be determined and the overall average values for all of the known lesions also will be recorded. The changes in SUV and T/N between the baseline and post estradiol challenge FFNP-PET/CT images will be compared in responders and nonresponders. Volumes of interest (VOIs) will be drawn around the entire lesion with the knowledge of the location of the tumor. SUV_{max} will be determined within the VOI. In addition, a similar volume of interest will be drawn in a comparable normal tissue region. The T/N ratio will be calculated by dividing the SUV_{max} of the tumor by the average SUV of normal comparable tissue. The absolute change and the percent change in uptake of ^{18}F -FFNP will be assessed semi-quantitatively and correlated with the clinical and radiologic results and subsequently with the results of the clinical follow-up evaluation. In patients with multiple lesions, the uptake of up to 5 lesions, selected as the most intense lesions seen on PET, will be determined and the overall average values for all of the known lesions also will be recorded. In addition, in patients with multiple lesions, SUV_{max} and T/N ratio will be measured for all known measurable lesions to assess within-patient heterogeneity in ^{18}F -FFNP uptake. Considering the optimum cutoff value for ^{18}F -FFNP uptake that distinguishes responders from nonresponders, lesions will be classified as ^{18}F -FFNP+ for lesions with ^{18}F -FFNP uptake at or greater than the cutoff value and ^{18}F -FFNP- for lesions with ^{18}F -FFNP uptake below the cutoff value. The changes in SUV and T/N after treatment will be compared in responders and nonresponders. The results of the PET studies will not be provided to the patient or the treating oncologist (see above). Clinical follow-up will provide information on tumor response, which will then be correlated with the sequential PET results to determine if these are predictive of ultimate response to estrogen therapy.

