10.0 STATISTICAL CONSIDERATIONS

10.1 Study Objectives and Endpoints

The primary endpoints of the study are the change in ^{18}F -FFNP uptake following one-day of estradiol measured as the SUV, T/M and tumor-to-normal tissue ratio (T/N), and the response to ET among cancer patients (responders vs. non-responders). The secondary endpoint of the study is the immunohistochemical (IHC) determination of PgR status (PgR+ vs. PgR-) in ER+ breast carcinoma.

Study Design: This is a pilot study aiming to evaluate if response to ET of breast cancer can be predicated by the changes in tumor uptake of ^{18}F -FFNP after a one-day estradiol challenge test. The sampling method is non-random. The change of ^{18}F -FFNP uptake after estradiol will be correlated with responsiveness to ET. Additionally, an optimal threshold of the change in ^{18}F -FFNP uptake will be developed to differentiate therapy responding and non-responding patients. Also, the change in ^{18}F -FFNP uptake after estradiol challenge will be compared with the IHC determination of PgR status with respect to the prediction of ET responsiveness.

Accrual: The rate of accrual for the study is expected to be about 1 - 2 patients per month. It is expected that the accrual period of the study will be completed in 30 months with total 50 patients enrolled.

Power Analysis: It is estimated that the response rate to ET in the recruited patients will range from 20-50%. Using a 2-sided independent t-test with 80% power at a 0.05 significance level, a sample of 10 responders vs. 40 non-responders (i.e., 20% response rate) will allow us to detect a minimum of 101% SD between-group difference, where SD represents a pooled standard deviation of the ^{18}F -FFNP uptake changes among both therapy responding and non-responding patients; and a sample of 25 responders vs. 25 non-responders (i.e., 50% response rate) will allow us to detect a minimum of 80.9% SD between-group difference.

Data Analysis: Demographic and clinical characteristics of all the enrolled patients will be summarized using descriptive statistics. The changes in ^{18}F -FFNP uptake after estradiol challenge will be compared between responders and non-responders via

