Wilcoxon rank sum test. A receiver operating characteristic (ROC) curve will be plotted to identify an optimal threshold of ^{18}F -FFNP uptake change to determine a criterion for the future prediction of therapy responsiveness. The positive and negative predictive values (PPV and NPV) will be calculated for response to ET using both the ^{18}F -FFNP uptake-based criterion and IHC determination of PgR receptor status. Multivariate logistic analyses of therapy response will be used to examine prediction power among the changes in ^{18}F -FFNP uptake and PgR receptor status

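### The FFNP+/FFNP- lesion label in Section 6.5 rests on a response cutoff that the plan derives only for change in uptake, so it cannot define baseline FDG+/FFNP- discordance

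*Combined protocol and SAP*

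**What the plan says.** - **The cutoff that is derived.** Objective 2.1.1 is to "Determine the optimum cutoff value for change in tumor" FFNP uptake after estradiol. The Study Design paragraph of Section 10.1 plans "an optimal threshold of the change in" uptake. The Data Analysis paragraph plots one ROC curve for FFNP "uptake change to determine a criterion for the future prediction of therapy responsiveness". All three concern change.
- **The cutoff that is used.** Section 6.5 refers to an optimum value for FFNP "uptake that distinguishes responders from nonresponders, lesions will be classified as" positive or negative. Positive means "uptake at or greater than the cutoff value and" negative means below it. The sentence does not mention change, and it names neither the scan (baseline or post-estradiol) nor the metric (SUVmax or T/N).
- **Where the label is needed.** Objective 2.2.1 maps active disease on FDG-PET/CT at baseline and states that "FDG+/FFNP- will be considered as discordant lesions". It also sets out to explore whether response is related to heterogeneity of uptake.
- **The other FFNP reading.** Section 6.5 says that the FFNP-PET/CT "images will be evaluated by one observer qualitatively". It gives no criterion for a positive or negative read and does not link this read to the lesion label.

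**The concern.** The Section 6.5 rule describes its cutoff in almost the same terms as objective 2.1.1, so a reader will look to 2.1.1 and Section 10.1 for the value. There the reader finds a threshold for a difference between two scans, while the rule compares it with uptake itself and 2.2.1 needs a label from the first scan alone.

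What is at stake is the baseline discordance result and any link drawn from it to response. If the rule stays as it is, whoever analyses the data must choose the threshold, the scan and the metric afterwards, possibly with response already known. Section 7.1 schedules the image analysis form about 24 weeks after the challenge scan, close to the response assessment at 6 months or later in Section 6.8. The baseline FDG scan, whose stated role in 2.2.1 and Section 5.2 is to map metabolically active disease, would then feed a comparison without a defined endpoint.

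**Working it through.** **1. The plan's own design figures.** Section 10.1 gives minimum detectable differences of 101% SD (10 vs 40) and 80.9% SD (25 vs 25), for a two-sided t-test at 0.05 with 80% power.
- Noncentral t: 1.011 SD and 0.809 SD. Power at the stated differences is 79.9% and 80.0%.
- Normal approximation, (1.960 + 0.842) × √(1/n₁ + 1/n₂): 2.802 × √(1/10 + 1/40) = 0.991 SD, and 2.802 × √(2/25) = 0.792 SD.

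The stated figures reproduce. They concern change only and do not depend on the lesion label.

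**2. The definitions side by side.**

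| Place | Quantity | Unit classified | Scans needed |
|---|---|---|---|
| 2.1.1 and 10.1 | change in uptake | patient response | both |
| 6.5 lesion rule | uptake | lesion | not stated |
| 2.2.1 discordance | FFNP- at baseline | lesion | baseline only |

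No section derives or pre-specifies a threshold for the level of FFNP uptake on either scan.

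**3. Each way of reading the 6.5 rule.**

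(a) *The 2.1.1 change cutoff is compared with a baseline level.* The scales do not interchange. The documents give no FFNP cutoff, so as an assumption borrow the 12% increase used for FDG in Section 1.3, and assume baseline levels from 1 to 5. Entered as 12, it makes every lesion FFNP-, because 5 < 12. Entered as 0.12, it makes every lesion FFNP+, because 1 > 0.12. The label then reflects the choice of unit. An absolute-change cutoff shares its unit with the level but measures something else: a lesion with high, unmoving uptake can pass, and one with low uptake that rises steeply can fail.

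(b) *Uptake is shorthand for change in uptake.* The rule is then coherent, but it labels each lesion's response to estradiol. That needs the second scan, so it cannot define FFNP- at baseline.

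(c) *A separate level cutoff is meant.* No objective, endpoint or analysis derives it. If it were chosen as the level that best separates responders from nonresponders in the same patients, low-uptake lesions would be concentrated among nonresponders partly by construction. Relating discordance to response under 2.2.1 would then partly return the rule used to set the label.

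(d) *The qualitative read supplies FFNP-.* No positivity criterion is stated, and Section 6.5 ties the label to the cutoff instead.

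None of the four readings yields a usable baseline label.

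**4. A contrast inside the document.** The FES and FDG work described in Section 1.3 kept the two kinds of threshold apart: an SUV level of at least 2 for baseline FES, and an increase of at least 12% for FDG after estradiol.

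**The case against.** The strongest reply is that Section 6.5 never says that a change cutoff is applied to a level. Elsewhere the same section says change when it means change, so the literal sense of the rule is a level cutoff that Section 10.1 failed to specify. On that view this is an omission and no scale error has been made. The part that stands is that a reader who infers a definite scale error goes beyond the text. The point does not need that inference, because the literal reading leaves the level cutoff underived and, since it is described as separating responders from nonresponders, circular for 2.2.1.

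A second reply is that heterogeneity can be studied without the label. This is right. Section 6.5 measures SUVmax and T/N for all known measurable lesions for that purpose, and the comparison of the two FFNP scans in 2.2.1 needs no baseline sign. A reader might infer that objective 2.2 fails as a whole; the documents do not support that.

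A third reply is that FDG+/FFNP- could be a visual mismatch. Objective 2.2.1 does not cite the 6.5 cutoff, so this is possible, but without a stated visual criterion it does not close the gap.

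Finally, this is a pilot study and 2.2.1 is worded as exploration. That limits the weight of the point without removing it.

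**Conclusion.** The point holds, within limits. Under every reading considered, the stated rule does not give a valid FFNP- label at baseline, so baseline FDG+/FFNP- discordance and its relation to response are not defined by the plan. The rule itself needs correcting, because following it leads either to a label of the wrong kind or to a threshold tuned to the outcome. The scope is the +/- label and the exploratory baseline discordance analysis. The responder/nonresponder comparison of change, the ROC analysis of change, the predictive values and the power figures do not depend on it.

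No numerical size can be given. A reader might use the mouse tumor-to-muscle ratios in Section 1.3 (3.6 rising to 6.9, a change of 6.9 − 3.6 = 3.3) to argue that untreated lesions would nearly all be FFNP+ and discordance would fall towards zero. That does not follow. The ratios are averages in an endocrine-responsive animal model, while the patient measures are SUVmax and T/N. A mean above a cutoff does not give the share of lesions below it. The direction also depends on the metric and unit, as step 3(a) shows. Nor are the FES discordance figures of 24% and 28% of patients in Section 1.2 a benchmark, since they concern another tracer, another definition and patients, not lesions.

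The circularity argument assumes that a level cutoff would be fitted to response in the same patients.

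**What to change.** Split the rule in Section 6.5 and carry the wording into 2.2.1 and Section 10.1.

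- **Baseline discordance.** Define FFNP+ and FFNP- on the baseline scan by a criterion that does not use response, and name the metric. Two options are lesion T/N against comparable normal tissue, or the qualitative read made without knowledge of outcome and with a written visual criterion. Fix it before outcomes are known. Report discordance over a stated range of the threshold, because the documents give no human FFNP threshold; Section 1.2 reports only a difference between PgR+ and PgR- tumors (p = 0.001).
- **Response to estradiol.** Use the 2.1.1 change cutoff only to label each lesion's response on the second scan, naming the metric and whether the change is absolute or percent.

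Keep the continuous SUVmax and T/N description of heterogeneity as it is.

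The cost is wording only, with no added patients, scans or procedures. The downside is that the level criterion must be chosen in advance and will be somewhat arbitrary, which is why the sensitivity range is needed.

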
6.6 Toxicities Related to ^{18}F -FDG & ^{18}F -FFNP PET/CT Imaging

Likely:

- Mild discomfort from the placement of the IV in the patient's arm.

Less Likely:

- Discomfort from lying still on the imaging table.
- There is a slight risk of bruising at sites of vein puncture.

Rare:

- There is a remote risk of infection and an even smaller risk of blood clot at the site of the IV placement
- There is a rare possibility of an allergic-type or other adverse reaction to radioactively labeled drugs. While none have been reported to date with the

radioactive materials ^{18}F -FFNP or ^{18}F -FDG, such a reaction could be serious and may result in death.

- **RADIATION EXPOSURE FROM PET/CT IMAGING:** the amount of radiation exposure the patient will receive from one injection (15mCi) of ^{18}F -FDG and the CT scan for attenuation correction is equivalent to a uniform whole body exposure of approximately 1.51 rem. The amount of radiation exposure from ^{18}F -FFNP injection and the CT scan for attenuation correction is equivalent to a uniform whole body exposure of approximately 1.39 rem. Patients will be scanned on 2 separate occasions with FFNP plus one FDG scan resulting in a total exposure of 4.28 rem.

6.7 Toxicities Related to Estradiol Challenge

Because of the low dose and single administration toxicities from the estradiol challenge are not expected. The following side effects have been reported by patients taking estradiol as treatment for breast cancer over an extended period of time:

Likely/Common

- upset stomach
- nausea
- vomiting
- changes in appetite
- generalized feeling of weakness or fatigue
- fever
- headache

Less Likely/Less Common

- weight gain
- fluid retention
- insomnia (unable to sleep) or drowsiness
- vaginal discharge
- spotting to darkening of the skin
- breast discomfort or enlargement

Rare

- uterine fibroids
- stroke
- blood clots
- allergic reaction and symptoms such as-unexplained rash, itching, hives, and swelling, irregular heartbeat, difficulty breathing and shortness of breath.
- There is a rare possibility that the administration of estrace will cause symptoms of clinical flare. Clinical flare can occur with any hormone used in the treatment of breast cancer. Physicians recognize that women who experience a

clinical flare are likely to benefit from hormone therapy. Clinical flare is a temporary worsening of the symptoms associated with your breast cancer such as increased bone and joint pain.

6.8 Evaluation of Tumor Response

The patients will be followed by their treating oncologist every 3 months per standard of care scheduling and not dictated by protocol (or earlier in case of a suspicion of early progression) until disease progression. Clinical benefit (complete response + partial response + stable disease) will be determined ≥ 6 months after initiation of therapy. Response will be evaluated according to RECIST 1.1 (Eisenhauer EA, Therasse P, Bogaerts J, et al. New response evaluation criteria in solid tumors: Revised RECIST guideline (version 1.1). *Eur J Cancer* 2009; 45:228-47). This evaluation will be based on the composite results of imaging studies (CT, MRI, bone scintigraphy, FDG-PET, etc.), serum tumor markers and evaluation of symptoms as deemed appropriate by the treating physician at the 6-month visit or at the time that there is evidence of clinical progression of disease, if before six months. Clinical response using RECIST version 1.1 by an oncologist will be defined as:

6.7.1 Complete Response:

Disappearance of all target lesions: Disappearance of all target lesions. Any pathological lymph nodes (whether target or non-target) must have reduction in short axis to <10 mm.

6.7.2 Partial Response (PR):

At least a 30% decrease in the sum of the longest diameter (LD) of target lesions taking as reference the baseline sum LD.

6.7.3 Progression (PD):

At least a 20% increase in the sum of the LD of target lesions taking as references the smallest sum LD recorded since the treatment started or the appearance of one or more new lesions.

6.7.4 Stable Disease (SD):

Neither sufficient shrinkage to qualify for PR nor sufficient increase to qualify for PD taking as references the smallest sum LD since the treatment started. Patients having a documented response with no reconfirmation of the response will be listed with stable disease.

6.7.5 Osseous disease only or osseous-dominant disease:

For patients with osseous metastasis only, a complete response was defined as disappearance of all objective and clinical disease, including complete normalization of radiological studies and tumor markers. A partial response was defined as a decrease in pain with evidence of recalcification of known osseous lesions on radiography. Disease progression was defined as worsening of disease on nuclear medicine scan or radiographs or worsening of pain and decline in

performance status. Any response that did not meet the criteria for complete response, partial response, or progression was defined as stable disease.

